4.1.4 Able to read and comprehend English

4.2 Exclusion Criteria

4.2.1 Current diagnosis of epilepsy, dementia, or other neurologic disease that may prevent use of VR headset and software

4.2.2 Sensitivity to flashing light

4.2.3 Diagnosis of motion sickness

4.2.4 Pregnancy or a medical condition where the study participant is prone to frequent nausea or dizziness

4.2.5 Current or recent (less than 6 months) use of opioids

4.2.6 Individuals with psychiatric disorders, including those with delirium or other disorders that may involve hallucinations or psychosis

5.0 TREATMENT PLAN

5.1 Treatment Dosage and Administration

5.1.1 Pre-op visit:

Eligible women will sign the study consent form at one of their pre-operative appointments. During this visit, a study staff member will explain the use of the VR goggle set by watching a short VR experience of swimming with dolphins, lasting approximately 2 minutes. The study participant and/or a member of their family will be shown how to use the device and how to recharge the battery, if needed. At this time, the patient will be offered the opportunity to test a VR set. Study participants will be advised that standing puts them at risk for a fall, and that they should remain seated for each VR intervention. An interval of 15 minutes is suggested for first-time use, but study participants will be allowed to continue as long as they are not experiencing any discomfort or side effects (dizziness, motion sickness, etc.).

We will keep a log of reasons for eligible patients who decline study participation.

5.1.2 After surgery:

After surgery, and once alert, the study participant can start using VR. The participants will be instructed to use VR the first time they feel pain and prior to requesting/taking opioids. They will be instructed to repeat that at least within 3 hours of first usage, the morning after the operation and once before discharge and any time they feel pain. Study participants will be instructed to

use the VR every time they feel pain and before asking for a pain medication. They can take pain medications, if they choose to do so.

Compliance to the protocol will be monitored using software for the VR modules and remote data uploads of activity. Additionally, study participants will be asked to log the time and duration of VR usage (appendix 2).

Pain ratings and pain medication usage history throughout hospitalization will be retrieved from the EHR by study staff. Pain rating scales and collection of medications will be done as per standard of care, and this information will then be pulled from the medical records.

5.1.3 Post-op visit:

Patient Semi-Structured Interview:

At one of their post-op visits at the Breast Center, using the provided patient interview script on Appendix 1, patients will be asked questions regarding their experience with VR. Responses will be written down by the study staff.

5.2 Use of Opioids

In order to capture medication use related to their injury, including the use of opioids, we will link patient electronic health record (EHR) data to the other data sources using Medical Record Numbers and date of birth. We will collect opioids information using CSLINK. Prescribed opioid medications include: codeine, dihydrocodeine, morphine, hydromorphone, oxymorphone, tapentadol, buprenorphine, methadone, oxycodone, fentanyl, remifentanil, and hydrocodone. Tramadol usage will also be included. We will convert all opioid doses into a single metric using morphine milligram equivalents (MME).

5.3 Risks

Women using the virtual reality intervention may experience side effects common to users of VR and individuals who view 3D video, including motion sickness, dizziness, eye strain, headaches, or other visual abnormalities. If a study participant experiences these symptoms, she will be asked to stop using the VR software for 15 minutes and will be allowed to continue if she wishes to proceed. A small number of patients (up to 0.025%) may experience seizures or severe symptoms (e.g., disorientation, nausea, or drowsiness) upon viewing the virtual reality experience. Seizures from flashing light are more common in children and epileptic patients (who are excluded). To minimize this concern further, we have not incorporated flashing lights into the VR experiences. Some study participants may find the VR goggles uncomfortable to wear or confining. To date, patients with claustrophobia have not reported discomfort using VR goggles, as they are often used in treatment of that condition. Nevertheless, individuals previously diagnosed with claustrophobia should discontinue use if they feel uncomfortable. A trained study staff member will be available during initial use to ensure safety. Study participants who use the VR headset over several days are instructed to use it for a maximum of 30 minutes at a time. In pilot testing, patients have not reported any adverse effects from extended use of VR hardware. Subjects may feel uncomfortable when answering survey and interview questions. If subjects are uncomfortable answering any survey question, they may skip it. The survey will be labeled with a unique study number so that only the research team can identify subjects.

5.4 Duration of Study Participation

The study duration for each study participant will start prior to surgery and will end after their post-op visit once the interview has been conducted.

5.5 Subject Replacement

Subjects who withdraw from the study treatment prior to starting study intervention will be replaced.

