3.0 STUDY DESIGN

We will conduct a pilot study of VR non-opioid management for women undergoing mastectomy and implant-based reconstruction. Study participants will receive specialized VR interventions, administered via VR headsets, to manage pain.

Historical control patients of the study investigators, who have undergone mastectomy and implant-based reconstruction between October 2008 to October 2018, will be identified by the Cancer Registry, according to the study eligibility criteria, and matched based on the following criteria:

- Age and gender
- Prophylactic or cancer
- Pre- or post-pectoral approach
- Sentinel biopsy, axillary dissection, or no nodal surgery
- Use of Paravertebral Block Analgesia (PVB)
- Neoadjuvant therapy or not

The matching will be done by the study statistician. Prior to sending the log to the statistician, the Cancer Registry database will be deidentified by the study staff and coded to ensure patient confidentiality. This portion of the study this is a retrospective data analysis and a waiver of consent and HIPAA authorization will be requested to review and collect data from these patients' medical records.

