6.1.3 Review subject eligibility criteria

6.2 Procedures During Treatment

Pain scores will be recorded using pain scores reported to the care providers and entered in the EHR.

Opioid use will be collected via information recorded in the EHR (CS-Link). Study participant will be approached at their post-op visit to complete study questionnaires as well as the study interview.

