6.3 Removal of Subjects from Study

Patients can be taken off the study treatment and/or study at any time at their own request, or they may be withdrawn at the discretion of the investigator for safety, behavioral or administrative reasons. The reason(s) for discontinuation will be documented and may include:

- 5.5.1 Patient voluntarily withdraws (follow-up permitted);
- 5.5.2 Patient withdraws consent (termination of treatment and follow-up);
- 5.5.3 Patient is unable to comply with protocol requirements;
- 5.5.5 Patient experiences toxicity that makes continuation in the protocol unsafe;
- 5.5.6 Treating physician determines continuation on the study would not be in the patient's best interest;

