Patients can pick and choose which visualizations to watch based on their own preferences. In clinical testing, we asked patients to use the headset at least thrice daily, for 15 minutes per treatment period, and to also use as needed for breakthrough pain between treatments. The appliedVR software allows our team to monitor adherence with the therapy, including the visualizations selected by the user, the amount of exposure time, and the time of day the visualization was viewed.

Using Samsung Gear goggles, participants will be shown a short VR experience of swimming with dolphins, lasting approximately 2 minutes. During your pre-op visit, a study staff member will show the participants how to use the VR goggles and connected smartphone and answer any questions about them.

They will be asked to watch VR only once after they wake up after surgery, and any time they feel pain. We recommend taking short, 5-10-minute breaks after 30 minutes of use, but they may continue afterward. This experience is an addition to usual care in the hospital and will not impact any additional care the participants receive at CSMC.

We will also obtain pain ratings, participants' use of pain medication while recovering from the surgery, and any physical symptoms they report to the nurse throughout your stay. Recording all of this information is standard of care. It is not being done for research. We will review medical records to obtain this type of information.

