8.0 STATISTICAL CONSIDERATIONS

8.1 Sample Size

This is an exploratory pilot study to estimate the effect of VR on opioid use during the stay. We will enroll 20 eligible patients to this study. We will include data from 20 patients for the historical control portion of the study matched 1 to 1 on age, surgery type, use of neoadjuvant therapy, and use of paravertebral block analgesia. Assuming a standard deviation of 1, a sample size of 20 matched pairs would produce a confidence interval with a distance from the mean to the limits that is equal to 0.468 for the difference in requested pill count.

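### Does replacing women who withdraw before the intervention starts bias the comparison with the matched historical controls?

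*Combined protocol and SAP*

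**What the plan says.** Section 5.5 is a single sentence: "Subjects who withdraw from the study treatment prior to starting study intervention will be replaced". The start of the intervention is not defined there or elsewhere.

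Two readings are open. Section 5.1.1 has a short VR demonstration at the pre-operative visit, and "At this time, the patient will be offered the opportunity to test a VR set". Section 5.1.2 says: "After surgery, and once alert, the study participant can start using VR". Section 7.0 points the same way: "They will be asked to watch VR only once after they wake up after surgery, and any time they feel pain". The post-operative reading is the more natural one.

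On follow-up, section 6.3 lists as one reason for discontinuation "Patient voluntarily withdraws (follow-up permitted", and separates it from withdrawal of consent, which ends both treatment and follow-up. On data, section 6.2 says: "Opioid use will be collected via information recorded in the EHR (CS-Link".

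On the comparison, section 3.0 says the historical controls "will be identified by the Cancer Registry, according to the study eligibility criteria, and matched based on the following criteria". Section 8.1 plans 20 enrolled patients and says: "We will include data from 20 patients for the historical control portion of the study matched 1 to 1 on age, surgery type". Section 9.2 (Data Analyses/Study Endpoints) specifies a paired t test on the matched pairs and complete-case handling of missing data. It names no analysis population.

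**The concern.** The primary endpoint is opioid use during the stay, and that period opens before first VR use. If the start means first post-operative use, the replacement rule acts inside the endpoint window. A woman with a hard first few hours might withdraw, be replaced, and leave the comparison with her opioid use unread. No historical control is removed in this way. Matching on age, surgical factors and neoadjuvant therapy would not correct a selection on early post-operative course.

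The count in section 8.1 appears to reinforce this. With 20 patients and 20 controls matched one to one, a woman whose place has been refilled has no control set aside for her in the paired test.

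At stake is a shift in the estimated VR effect. It would favour VR if early withdrawers use more opioids than the women who stay, and count against VR if they use fewer.

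**Working it through.** **The plan's own figure.** Section 8.1 gives a half-width of 0.468 for 20 pairs and a standard deviation of 1. The confidence level is not stated; two-sided 95% reproduces the figure:

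t(0.975, 19)/√20 = 2.093/4.472 = 0.468.

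Replacement keeps 20 pairs and so keeps this precision. Only bias is in question.

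**Inputs that must be assumed.** The documents give no withdrawal rate and no opioid data for withdrawers. Let k be the number of women replaced after surgery whose data are then left out. Let D be the amount by which their mean paired difference exceeds that of the 20 analysed, in SDs of the paired difference. Compared with keeping all 20 + k women,

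bias = k/(20 + k) × D.

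Coverage of the nominal 95% interval comes from the non-central t distribution with 19 df and non-centrality bias × √20.

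| k | D | Bias (SD) | Share of 0.468 | Coverage |
|---|---|---|---|---|
| 0 | any | 0 | 0% | 95.0% |
| 1 | 0.5 | 1/21 × 0.5 = 0.024 | 5% | 94.9% |
| 2 | 0.5 | 2/22 × 0.5 = 0.045 | 10% | 94.6% |
| 3 | 0.5 | 3/23 × 0.5 = 0.065 | 14% | 94.1% |
| 3 | 1 | 3/23 × 1 = 0.130 | 28% | 91.4% |

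A negative D gives the same sizes with the sign reversed.

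**How large could D be?** Take the extreme case in which the k women replaced are exactly the k highest opioid users among 20 + k, with normal outcomes and no VR effect. In a simulation of 200,000 sets, k = 3 gives a largest D of 1.25 if outcomes within a pair are uncorrelated and 0.89 if their correlation is 0.5. The bias is then 3/23 × 1.25 = 0.16 SD (35% of the half-width) or 3/23 × 0.89 = 0.12 SD (25%). At correlation 0.5, D = 1 cannot be reached even with perfect selection. Strongly skewed outcomes could raise these ceilings; that was not computed.

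**How plausible is k?** k = 3 means 3 of 23 women, or 13%, formally withdrawing between surgery and first VR use. That window is short, because VR is to be used on waking or at first pain. Section 5.1.2 also lets a participant take pain medication if she chooses, so a woman who does not want the headset has no need to withdraw. Non-use is not withdrawal and does not trigger replacement.

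**Does the text exclude her data?** Section 5.5 governs headcount only. A woman who stops VR but allows follow-up still has her opioid use in the hospital record, so complete-case handling does not remove her. The controls come from a registry covering October 2008 to October 2018 and are matched by the statistician, so matching one more is a small task.

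**The case for a change.** The best argument for a change is that it would be cheap and is best made before any data are seen. The start is undefined, the post-operative reading is the natural one, and no sentence assigns a replaced woman to the analysis. Defining the start and analysing every consented woman who has the surgery would close off a later choice about who counts, with no new data collection.

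The textual part of this stands: the definition and the analysis set are not written down. The proposed remedy is less secure. The objective in section 2.0 concerns the effect of utilizing VR, in an exploratory pilot with no randomisation to protect. Making all operated women the primary set is one defensible estimand, but it dilutes the estimate with women who never used VR, and nothing in the documents requires it. Limiting replacement to cancelled operations and pre-operative withdrawal of data permission goes further than the problem does. A woman who gives up VR before surgery but lets her data be used could no longer be replaced, although her decision cannot depend on a post-operative course that has not happened. Nor would either step touch the larger difference between consenting volunteers and historical controls.

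**Conclusion.** No change to the plan follows. The gap is real but is a matter of unwritten detail. Harm requires that the start means post-operative use, that a woman formally withdraws in a short window, that her available data are left out although the plan does not say so, and that early withdrawal tracks opioid need. If the first or third condition fails, this bias does not arise. If all four hold, one to three replacements with D = 0.5 shift the estimate by 0.02 to 0.07 SD and cost less than one percentage point of coverage. The ceiling for three replacements under perfect selection is 0.12 to 0.16 SD, still well inside the planned half-width of 0.468. These sizes rest on assumed k and D, and the ceiling also on normal outcomes. A sensible analyst would report any replacements with their timing and reasons, and would use the hospital opioid data of a woman withdrawn after surgery where her consent allows. The stronger step of redefining the primary set is a trade-off between estimands, not the correction of an error.

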6.0 STUDY PROCEDURES

6.1 Screening/Baseline Procedures

6.1.1 Informed Consent

Eligible subjects will be identified by the investigators and research staff according to the eligibility criteria. Subjects will be asked to sign and date the Informed Consent and HIPAA Authorization form after receiving a complete explanation of the research study including risks, benefits, and alternatives to participation. Eligible subject must have the ability to understand and the willingness to sign a written informed consent document.

6.1.2 Demographics

Name, medical record number, age, gender, race/ethnicity obtained from medical records

6.1.3 Review subject eligibility criteria

6.2 Procedures During Treatment

Pain scores will be recorded using pain scores reported to the care providers and entered in the EHR.

Opioid use will be collected via information recorded in the EHR (CS-Link). Study participant will be approached at their post-op visit to complete study questionnaires as well as the study interview.

6.3 Removal of Subjects from Study

Patients can be taken off the study treatment and/or study at any time at their own request, or they may be withdrawn at the discretion of the investigator for safety, behavioral or administrative reasons. The reason(s) for discontinuation will be documented and may include:

- 5.5.1 Patient voluntarily withdraws (follow-up permitted);
- 5.5.2 Patient withdraws consent (termination of treatment and follow-up);
- 5.5.3 Patient is unable to comply with protocol requirements;
- 5.5.5 Patient experiences toxicity that makes continuation in the protocol unsafe;
- 5.5.6 Treating physician determines continuation on the study would not be in the patient's best interest;

7.0 Virtual Reality

7.1 We will use a Samsung Gear VR goggle set, fitted with a Samsung Galaxy phone that delivers VR images and sound. Samsung Gear was selected because it is commercially available, widely used, relatively inexpensive, has minimal visual latency, and offers a generally positive patient experience based on our previous research. [8]

We will use the appliedVR app to offer >30 therapeutic VR experiences through the headsets. Our team has worked with appliedVR to curate experiences that are acceptable to a wide range of patients. The app includes a menu of visualizations, each mapped to a therapeutic benefit (e.g. pain reduction, anxiety reduction, mindful meditation).

The app includes "Pain RelieVR", a 15-minute VR experience specifically designed to treat pain in patients with limited mobility. Pain RelieVR is an immersive, 360-degree game experience that takes place in a fantasy world where the user attempts to shoot balls at a wide range of moving objects by maneuvering their head towards the targets. This engaging, medium-intensity activity is free of interruption, offering the user a distracting experience designed to reduce the perception of pain. Pain RelieVR is a non-violent and non-competitive game that incorporates motivational music and features positively reinforcing sounds, animation and direct messages to patients. Forward-facing action allows patients with limited mobility to engage without having to turn backwards or contort into potentially uncomfortable positions.

The app also includes "Anxiety RelieVR," an interactive, meditative landscape along a peaceful shoreline. In contrast to Pain RelieVR, which acts through distraction therapy, Anxiety RelieVR employs mindful meditation to help manage the affective component of pain. These cornerstone experiences are supported by a wide range of additional therapeutic journeys, including an Iceland flyover in a helicopter, an undersea experience, and a variety of nature-related experiences, among many others.

Another option is "EaseVR" which is a new meditation VR experience that is currently being used in several pain studies within Cedars-Sinai and beyond. During the program the patient can be in 8 different environments while a narrator who is an expert in meditation walks through the experience. The patient will have a microphone to deep breath with the meditation program.

Patients can pick and choose which visualizations to watch based on their own preferences. In clinical testing, we asked patients to use the headset at least thrice daily, for 15 minutes per treatment period, and to also use as needed for breakthrough pain between treatments. The appliedVR software allows our team to monitor adherence with the therapy, including the visualizations selected by the user, the amount of exposure time, and the time of day the visualization was viewed.

Using Samsung Gear goggles, participants will be shown a short VR experience of swimming with dolphins, lasting approximately 2 minutes. During your pre-op visit, a study staff member will show the participants how to use the VR goggles and connected smartphone and answer any questions about them.

They will be asked to watch VR only once after they wake up after surgery, and any time they feel pain. We recommend taking short, 5-10-minute breaks after 30 minutes of use, but they may continue afterward. This experience is an addition to usual care in the hospital and will not impact any additional care the participants receive at CSMC.

We will also obtain pain ratings, participants' use of pain medication while recovering from the surgery, and any physical symptoms they report to the nurse throughout your stay. Recording all of this information is standard of care. It is not being done for research. We will review medical records to obtain this type of information.

8.0 STATISTICAL CONSIDERATIONS

8.1 Sample Size

This is an exploratory pilot study to estimate the effect of VR on opioid use during the stay. We will enroll 20 eligible patients to this study. We will include data from 20 patients for the historical control portion of the study matched 1 to 1 on age, surgery type, use of neoadjuvant therapy, and use of paravertebral block analgesia. Assuming a standard deviation of 1, a sample size of 20 matched pairs would produce a confidence interval with a distance from the mean to the limits that is equal to 0.468 for the difference in requested pill count.

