9.2 Data Analyses/Study Endpoints

Quantitative data will be expressed as mean \pm standard type or median with interquartile range, and categorical variables as counts and frequencies. We will use complete case analysis to manage missing data. All statistical analyses will involve the use of Excel. Descriptive statistics will be used to summarize pain scores and opioid use in the intervention and the historic control group. Average number of opioid pills requested will be compared between the study cohort and the historic control group. A paired t test will be used to compare the difference in average pill count between the two groups based on the matched pairs with historic controls. Confidence intervals for the number of pills and the secondary endpoints of reported pain scores, satisfaction, and length of stay will be calculated in the study cohort and for the historic controls.

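### Section 8.1 takes one historical control per VR participant from a ten-year chart source; if enough close matches exist, the 1:1 interval is about 15% wider than 1:2 matching would give and about 26% wider than 1:4.

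*Combined protocol and SAP*

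**What the plan says.** Section 8.1 fixes both groups. For the VR group: "We will enroll 20 eligible patients to this study". For the controls: "We will include data from 20 patients for the historical control portion of the study matched 1 to 1 on age", followed by surgery type, neoadjuvant therapy and paravertebral block. The only justification of size is precision: "Assuming a standard deviation of 1, a sample size of 20 matched pairs would produce a confidence interval" whose half-width is described as a "distance from the mean to the limits that is equal to 0.468 for the difference in requested pill count".

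Section 3.0 gives the source of the controls: "Historical control patients of the study investigators, who have undergone mastectomy and implant-based reconstruction between October 2008 to October 2018". They are found through the Cancer Registry under the study eligibility criteria and handled as a retrospective data analysis, for which a waiver of consent will be requested. The matching list in Section 3.0 is longer than the one in Section 8.1. It covers age and gender, prophylactic or cancer indication, pectoral approach, nodal surgery, paravertebral block and neoadjuvant therapy.

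Section 9.2 (Data Analyses/Study Endpoints) states the analysis: "A paired t test will be used to compare the difference in average pill count between the two groups based on the matched pairs". On missing values it says: "We will use complete case analysis to manage missing data". Neither document section gives the number of eligible charts or a reason for one control per participant.

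**The concern.** The VR participants must be enrolled one by one, and there are only 20. The controls already exist as charts. With one control each, equal variances and no within-pair correlation, half of the variance of a VR-minus-control difference comes from the single control. That half can be reduced without enrolling anyone.

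This matters because the study is meant to estimate an effect, and interval width is the only criterion that Section 8.1 offers for its size. A one-to-one ratio is the least precise choice if closer use of the chart source is possible.

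**Working it through.** **Inputs.** 20 VR participants, 20 controls at 1:1, SD of 1 and half-width 0.468 (Section 8.1); paired t test (Section 9.2, Data Analyses/Study Endpoints). The confidence level is not stated.

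**Step 1: reproduce the plan's figure.** Half-width = t(0.975, 19 df) × SD / √n = 2.093 × 1 / √20 = 2.093 / 4.472 = 0.468. The figure therefore rests on a two-sided 95% interval, with 1 taken as the SD of the within-pair difference. Other readings do not reproduce it: a normal quantile gives 0.438, a 90% level 0.387, and two independent groups with SD 1 each 0.640.

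**Step 2: variance with k controls per participant.** Let every value have variance σ², and let any two members of a matched set have correlation ρ. Then

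Var(VR − mean of k controls) = σ²[1 + (1 + (k − 1)ρ)/k − 2ρ] = σ²(1 − ρ)(1 + 1/k).

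At k = 1 this is 2σ²(1 − ρ), so the half-width relative to 1:1 is √((1 + 1/k)/2), whatever ρ is. There are still 20 set differences and 19 degrees of freedom, so the t quantile does not change.

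**Step 3: numbers.**

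| Ratio | Factor | Half-width | Narrower than 1:1 | 1:1 wider by |
|---|---|---|---|---|
| 1:1 | 1 | 0.468 | – | – |
| 1:2 | √0.750 = 0.866 | 0.405 | 13% | 15% |
| 1:3 | √0.667 = 0.816 | 0.382 | 18% | 22% |
| 1:4 | √0.625 = 0.791 | 0.370 | 21% | 26% |

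The last two columns describe the same ratio on different bases: 0.468/0.370 = 1.265, and 0.370/0.468 = 0.791. A simulation at ρ = 0.5 gave a 1:1 to 1:4 width ratio of 1.264.

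**Step 4: what 1:4 is worth.** At 1:1, 30 pairs give 0.373 and 31 pairs give 0.367. So 20 VR participants with four controls each match the precision of about 30 to 31 pairs.

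**Step 5: unequal variances, taking ρ = 0.** With r = control SD / VR SD, the 1:1 to 1:4 width ratio is √((1 + r²)/(1 + r²/4)). At r = 0.5 the 1:1 interval is 8% wider, at r = 0.75 it is 17% wider, and at r = 2 it is 58% wider. The gain is always positive, but 26% holds only at r = 1.

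**Step 6: a ratio that varies.** If participant i has kᵢ controls, the half-width is about 0.468 × √((1 + mean of 1/kᵢ)/2). As an illustration, suppose ten women have four matches and ten have one. The mean of 1/kᵢ is (0.25 + 1)/2 = 0.625, and the half-width is 0.468 × √0.8125 = 0.422.

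**The case against.** The strongest objection is feasibility. A reader might infer from the ten-year window that the source is known to support 1:4. The documents do not show this. Controls must be the investigators' own patients and meet the eligibility criteria. They must then agree on indication (2 levels), pectoral approach (2), nodal surgery (3), block (2) and neoadjuvant therapy (2), nominally 2 × 2 × 3 × 2 × 2 = 48 cells before age. This stands: the achievable ratio is unknown, and a woman with only one match contributes no gain.

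Second, 1:1 matching is a standard choice and this is an exploratory pilot. Section 8.1 sets no precision target, so no shortfall is shown, and its SD of 1 has no stated source. This also stands. The relative gain does not depend on that SD, but its value in pills cannot be judged from the documents.

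Third, more controls reduce random error only. Calendar year is not a matching factor, so drift in prescribing between 2008 and 2018 would bias a 1:4 comparison too, inside a narrower interval. That is a true limit, but the 1:1 plan draws on the same window and already carries that bias.

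Fourth, later matches may be less close. In an extreme case, the best match has correlation 0.5 with the VR value, the other three have none, and the controls are mutually uncorrelated. The 1:4 variance is then 1 + 1/4 − 2 × 0.5/4 = 1.0 (in units of σ²), the same as 2 × (1 − 0.5) = 1.0 at 1:1, and the gain is gone. Strict matching rules are therefore part of the proposal.

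A reader might also infer that 1:1 is fragile under complete case analysis, since a chart without opioid data removes the treated woman as well. Losing 2 pairs would give 0.497 and losing 3 would give 0.514. The documents do not support this as an argument for 1:4. They give no missing-data rate, they describe medication recording as standard of care, and nothing in Section 3.0 prevents replacing an unusable chart under 1:1.

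**Conclusion.** The point holds as a conditional, inexpensive improvement; 1:1 matching is not an error, and the plan's 0.468 is correct for the design it describes. If the pool holds enough close matches and variances are equal, the planned interval is about 15% wider than at 1:2 and about 26% wider than at 1:4. The 21% figure is how much narrower 1:4 would be, and should not be read as how much wider 1:1 is.

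The result assumes equal SDs in the two groups, equally close matches within a set and complete data. The pool size, which decides how much of the gain can be had, is not in the documents. The change would not make the historical comparison less biased.

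**What to change.** In Section 8.1:
- Count the eligible pool first.
- Match each VR participant to up to four controls who agree on every categorical factor in Section 3.0, with age within a caliper fixed in advance.
- Replace a control without a usable opioid record by the next match.
- Restate the half-width for the ratio achieved (0.405 at 1:2, 0.370 at 1:4, on the plan's SD). VR enrolment stays at 20.

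In Section 9.2 (Data Analyses/Study Endpoints):
- Run the paired t test on each VR value minus the mean of her matched controls. This remains feasible in Excel, the software that the plan names.
- Keep the best-match 1:1 comparison as a sensitivity analysis.
- State that additional controls do not address bias from the historical design.

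The cost is up to 60 more chart abstractions (80 − 20) and a waiver request that covers up to 80 records. Later matches may be slightly less close, which would shrink the gain; exact categorical matching and the age caliper limit this.
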